created for this project, on the same schedule as peer mentoring sessions. Both conditions will be delivered via Webex, which has several advantages for this intervention: 1) Sessions are easily accessible via phone or computer, allowing participants to choose their preferred interaction style; 2) A study coordinator can host the support groups and drop in/out for monitoring purposes; 3) There are video- or voice-call options for up to 25 participants at a time; and 4) This application ensures concordant delivery methods across both arms of the study and the ability to document the frequency that voice and video options are used to adjust for participant choices in analyses. All participants (mentees, mentors, and social support controls) will be assessed using validated measures of patient reported outcomes and clinical indicators of disease activity at baseline, mid-intervention (3 months from baseline), immediately post-intervention (6 months from baseline), and 6 months post-intervention (12 months from baseline). For each wave, outcomes for mentees randomized to the mentored group will be compared with the outcomes of mentees randomized to the support group. A booster session will be incorporated for all participants (mentored and support group) at 3 months post-intervention to encourage retention.[102]

B4c. Scientific Rigor: Assuming 3 post-randomization measurement time points, level of significance p=0.05, two-tailed comparison, correlation between pairs of measurements within participants (interclass correlation) no larger than p=0.7, AR(1) covariance structure, we estimate that 123 participants per group (total n=246) are needed to detect, with 80% power, a standardized effect size of 0.35sd with 20% inflation for attrition at 12 months. This study will apply strict principles of randomized clinical trials including randomization, blinding, careful tracking of all participants and intent-to-treat analyses to ensure robust and unbiased results.

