Power and Sample Size Justification: The sample size calculation and power analyses are based on the primary outcome of change in HRQOL between baseline and 12 months post intervention. The minimum sample size was based on detecting a clinically meaningful difference of 0.35 standard deviation units (medium effect) based on prior studies.[87,93,139-143] Essentially, this is equivalent to testing the interaction between time and group. Assuming 3 measurement time points, level of significance p=0.05, two-tailed comparison, correlation between pairs of measurements within participants (interclass correlation) no larger than p=0.6, compound symmetry covariance structure, we estimate that 123 participants per group (total n=246) are needed to detect, with 80% power, a standardized effect size of at least 0.35sd. This sample size includes a 20% inflation for attrition at 12 months. This effect size is robust enough to provide sufficient power for the outcomes listed under aims 1 and 2 and is consistent with data from our pilot study of 20 mentees and 7 mentors (see preliminary data). The pre-post differences in the outcomes (such as overall social support, positive social interaction, tangible support, vitality, emotional support, social functioning, general health, coping, etc), ranged from 0.35 to 0.88 standard deviation units. Although these calculations account for within patient clustering through the intera-class correlation mentioned above, clustering within mentors and mentees are assumed to have minimal intra-class correlation based on pilot data, especially since the cluster sizes would be at most 3 at a given wave. However, a multi-level model will be used in the analysis to verify this. Since the effect size planned is conservative, if the clustering leads to higher intra-class correlation, we would still be able to detect meaningful differences. We will also consider including mentor as a fixed effect in the model.

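### Clustering in the control support groups is missing from both the power calculation and the model, and the power paragraph states its correlation bound in the favourable direction

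*Combined protocol and SAP*

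**What the plan says.** The Power and Sample Size Justification is "based on the primary outcome of change in HRQOL between baseline and 12 months post intervention", and equates this with a time-by-group test. It states: "The minimum sample size was based on detecting a clinically meaningful difference of 0.35 standard deviation units". It assumes three time points and a within-person correlation "no larger than p=0.6, compound symmetry covariance structure, we estimate that 123 participants per group (total n=246) are needed to detect, with 80% power", with 20% inflation for attrition included.

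Section B4c (Scientific Rigor) gives the same 123 and the same 80% from other inputs: "Assuming 3 post-randomization measurement time points" and a correlation "no larger than p=0.7, AR(1) covariance structure, we estimate that 123 participants per group". It names no contrast.

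On clustering, the power paragraph says "clustering within mentors and mentees are assumed to have minimal intra-class correlation based on pilot data", noting that a mentor has at most 3 mentees in a wave. It adds "However, a multi-level model will be used in the analysis to verify this", and a possible fixed effect for mentor. It then gives an assurance: "if the clustering leads to higher intra-class correlation, we would still be able to detect meaningful differences".

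Under B4b (Study Overview) and Control Intervention (Support Group), the 50 controls in each of three waves interact every two weeks in support groups made for the project. The Webex platform takes up to 25 people at a time. The number and size of the groups are not stated. The account of the PALS pilot says that it had no control group. Planned enrolment is 150 per arm.

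**The concern.** Three things do not fit together.

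1. Women who talk with each other every two weeks for 24 weeks may come to resemble each other in quality of life and self-management. In the control arm they do so in groups that may be much larger than a mentor's set of mentees. The plan discusses the smaller clusters only, on the strength of a pilot that could not have informed the larger ones. A model that leaves the support groups out gives confidence intervals that are too narrow and a type I error above 5%. The margin in enrolment does not cure that.
2. For a change from baseline, a higher correlation helps. An upper bound on the correlation therefore states the best case and hides the side on which power is lost.
3. The same 123 and 80% are attached to two sets of assumptions that do not describe one calculation. The power paragraph also places its endpoint 12 months after the intervention, whereas the last visit is 12 months from baseline, which is 6 months after the intervention.

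**Working it through.** **Reproducing 123.** Inputs from the power paragraph: two-sided 0.05, 80% power, 0.35 SD, compound symmetry with correlation rho = 0.6. For change from baseline the variance factor is f = 2(1 - rho) = 0.80. Then n per arm = 2(1.960 + 0.842)² f / 0.35² = 128.1 × 0.80 = 102.5 completers, and 102.5 × 1.2 = 123.0. The figure reproduces. Dividing by 0.8, so that 102.5 complete after 20% loss, gives 128.1.

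**Section B4c.** With no contrast named, the nearest match is an assumption: the mean of three follow-ups under AR(1) 0.7. Here f = [3 + 2(2 × 0.7 + 0.49)]/9 = 0.753 and n = 96.5, which gives 116 with × 1.2 and 121 with /0.8 (up to 123 with the t distribution). A change contrast under AR(1) 0.7 has f = 2(1 - 0.7²) = 1.02 over two visit steps, or 2(1 - 0.7³) = 1.314 over three, giving 157 or 202 with × 1.2. So the two paragraphs reach 123 only through different contrasts and different attrition conventions.

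**Direction of the bound.** Power for 0.35 SD on the change contrast with 20% loss (98.4 or 120 completers per arm) is below. The mixed-model column uses generalised least squares with four visits and compound symmetry. The loss falls before month 3, evenly over follow-up, or after month 6.

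| Enrolled per arm | rho | Completers only | Mixed model keeping earlier visits |
|---|---|---|---|
| 123 | 0.6 | 78% | 80-81% |
| 123 | 0.5 | 69% | 71-72% |
| 150 | 0.6 | 86% | 87-88% |
| 150 | 0.5 | 77% | 79-80% |

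Counting completers, 80% power needs 2(1 - rho) ≤ completers/128.1. That means rho of at least 0.62 at 123 per arm (98.4/128.1 = 0.768) and at least 0.53 at 150 per arm (120/128.1 = 0.937).

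**Clustering.** The documents give no ICC and no group size. Assumed: ICC 0.01, 0.02 or 0.05 on the analysed contrast, the same in both arms; 5 mentees per mentor (150 over the roughly 30 mentors expected under Recruitment of Mentors); support groups of 10, or of 25 (the platform limit). The design effect is DE = 1 + (m - 1)ICC in each arm, and the variance of the difference is (0.80/120)(DE_mentor + DE_group).

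Worked case, ICC 0.02 with groups of 25: DE_mentor = 1.08 and DE_group = 1.48. The variance is 0.00667 × 2.56 = 0.01707, so SE = 0.1306. Then 0.35/0.1306 = 2.68, and power = Φ(2.68 - 1.96) = 76%.

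If the model includes mentors but not support groups, type I error = 2[1 - Φ(1.96 √((DE_mentor + 1)/(DE_mentor + DE_group)))]. Here √(2.08/2.56) = 0.901, which gives 7.7%.

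| ICC | Power, groups of 10 | Power, groups of 25 | Type I error, groups of 10 | Type I error, groups of 25 |
|---|---|---|---|---|
| 0.01 | 84% | 81-82% | 5.5% | 6.1-6.4% |
| 0.02 | 81% | 76-78% | 6.0% | 7.2-7.7% |
| 0.05 | 75% | 64-68% | 7.4% | 10.3-11.5% |

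All rows use 150 enrolled per arm, 120 completers and rho 0.6. Where a range is shown, the worse value uses enrolled cluster sizes (5 and 25) and the better value uses completer sizes (4 and 20). The groups-of-10 figures use enrolled sizes. These are large-sample figures, and a test that allows for few control clusters would have somewhat less power.

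**The case against.** The strongest reply is that 123 is only a minimum and 150 per arm will be enrolled. That stands: without clustering, 150 per arm gives 86-88% at rho 0.6 and about 80% down to a correlation near 0.5. Nothing here is a call for more patients, and 123 is not an arithmetic error.

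A reader might infer that the 80% belongs to no test at all, or that the trial is really powered for one comparison and will run another, a raw month-12 difference. The documents do not support that. The power paragraph names change in HRQOL and a time-by-group test. The AIM 1 analysis aims at change from baseline, includes the interaction and uses model contrasts. Its sentence on comparing least squares means at month 12 fits that reading. What remains is that B4c must be reconciled with the power paragraph. The AIM 1 example model, whose visits stop at month 6, must also be matched to the month-12 primary time point.

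On clustering, groups of 25 are a platform limit and not a planned size, and at ICC 0.01 power stays above 80%. The loss is therefore uncertain. The assurance about detectable differences does have a stated basis, pilot effects of 0.35 to 0.88 SD. Those were pre-post differences without a control group, and 0.35 SD is itself the difference called clinically meaningful, so lower power at 0.35 SD is lower power for exactly that difference.

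The plan is not silent on clustering. But its multi-level model is offered to check mentor clustering, and the clustering adjustment mentioned in the exploratory analyses names no level.

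**Conclusion.** The point holds and should be fixed. The omission of support-group clustering is certain. Its size is not, because it depends on an assumed ICC and group size: over the ranges shown, power at 150 per arm runs from 84% down to 64%, and type I error from 5.5% to 11.5% if the groups are left out of the model. The direction of the correlation bound is a matter of algebra for the plan's own contrast. It costs about 9 percentage points between rho 0.6 and 0.5 at either sample size, counting completers. The mismatch between B4c and the power paragraph, and the endpoint wording, are matters of reconciliation. The two primary outcomes of AIM 1, both tested at 0.05, raise a separate question that is not settled here.

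**What to change.** Keep N=300.

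1. State the planned number and size of support groups and record each control participant's group. Fit a support-group random effect in the control arm and a mentor random effect in the mentored arm, with small-sample degrees of freedom (for example Kenward-Roger).
2. Replace both power paragraphs with one calculation for the between-arm difference in change to month 12 from baseline, baseline-adjusted and using all four visits. Correct the endpoint wording, and make the AIM 1 example model match. Use a lower bound for the baseline-to-month-12 correlation, taken from the SLE registry if its quality of life measures allow. Take attrition as n/0.8, give a range of ICC and group size, and report power at 150 per arm as a range.
3. Delete the sentence that meaningful differences would still be detectable, or support it with that range.

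Baseline adjustment recovers some power. With f = 1 - rho² and 120 completers per arm, it gives 92% at rho 0.6 and 88% at rho 0.5 before clustering.

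The cost is SAP wording, one recorded identifier and possibly a registry extract, with no extra patients or visits. Choosing more, smaller support groups would add moderator sessions. The downside is that the stated power becomes a range, part of it below 80%.

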AIM 1: Determine the efficacy of a peer mentorship intervention in African American women with SLE on disease self-management and HRQOL. Analyses for Aim 1 will focus on estimation of efficacy as determined by: (a) change in quality of life; and (b) change in self-management. Estimates of effect sizes for outcome variables will be reported as point estimates (mean differences between pre-post measures. as appropriate) and interval estimates (95% CI) with two-sided p-vales denoting statistical significance to provide an indication of the presence of a clinically important treatment effect. [145,146] A p-value of 0.05 will be considered to be statistically significant. After studying the distributions of baseline characteristics. we will use a generalized linear mixed model regression model to determine if the intervention will produce a greater change in the main outcomes from baseline. This model will include time, treatment (along with their interaction), and covariates (including the amount of intervention received, demographic factors, medications, coping, depression, stress, anxiety, health literacy, trust, and social support) as fixed-effects. Using the amount of intervention, which is measured as an aggregate number of sessions completed or hours of interaction as a covariate would allow us to study the dose response. In the generalized linear mixed model (GLMM), we will use different link functions depending on the assumed distribution of the response variable. For binary outcomes, we will use logit link and for count outcomes we will use log link under a poisson or negative binomial distribution. For example, for the a given quality of life variable, HRQOL measured at baseline, month 3 and month 6, we will include intervention group, time, and time X intervention as the primary independent variables in the basic (unadjusted) model, and covariates that are not balanced at randomization (or a propensity score based on these covariates) will be added in the subsequent (adjusted) model to adjust for the possible confounding effect of these variables. Unadjusted and covariate-adjusted least squares means for each outcome variable will be compared at the primary time point (month 12) and at intermediate secondary time point (month 6) using appropriate model contrasts and the Tukey-Kramer adjustment for multiple comparisons for the secondary time points. These contrast comparisons, along with corresponding 95% CI, will provide estimates of the difference in outcome means (effect sizes) for the hypothesized comparisons.

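### The same 123 per group is derived from two incompatible covariance assumptions, only one of which supports it for the change endpoint, and the analysis model names no within-woman covariance

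*Combined protocol and SAP*

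**What the plan says.** Two current sections of the combined protocol and SAP justify the sample size.

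- **B4c, Scientific Rigor**: three post-randomization time points and a within-person correlation of at most 0.7. It continues: "AR(1) covariance structure, we estimate that 123 participants per group (total n=246) are needed to detect, with 80% power".
- **Power and Sample Size Justification**: three measurement time points and a correlation of at most 0.6. It continues: "compound symmetry covariance structure, we estimate that 123 participants per group (total n=246) are needed to detect, with 80% power".

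Both use two-sided 5% significance, 80% power, 0.35 SD and a 20% allowance for attrition. Only the second names an endpoint. It says the calculation is "based on the primary outcome of change in HRQOL between baseline and 12 months post intervention", and adds: "Essentially, this is equivalent to testing the interaction between time and group".

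B4b sets assessments at baseline and months 3, 6 and 12, and recruits 150 per group.

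For the analysis, AIM 1 of the Overview of Statistical Analysis Plan says: "we will use a generalized linear mixed model regression model to determine if the intervention will produce a greater change in the main outcomes". Time, treatment and their interaction are fixed effects, and least-squares means are compared at month 12 as the primary time point. AIM 2 notes that such models can handle correlated repeated measurements. Neither paragraph names a within-woman covariance structure, a rule for choosing one, or a robust standard error. The multi-level model in the power section addresses clustering by mentor, which is a separate matter.

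**The concern.** With three or more visits and non-zero correlation, constant correlation and geometrically decaying correlation cannot both hold. The choice matters most for a change from baseline to the last visit. The variance of that change depends on the correlation between the first and last visits, which is the pair AR(1) makes weakest.

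Two things are at stake. The first is the stated power: if B4c's structure is the right one, 123 per group is too few for the change endpoint. The second is the analysis: the simplest mixed model, a random intercept per woman, imposes compound symmetry. If correlation in fact decays, that model uses the average correlation over all visit pairs in place of the lower first-to-last correlation. The standard error of the change contrast is then too small.

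**Working it through.** **Inputs.** Two-sided alpha 0.05 (z = 1.96), power 80% (z = 0.8416), effect 0.35 with SD = 1, and an attrition factor of 1.2, all common to both sizing sections. Compound symmetry 0.6 comes from the power section, AR(1) 0.7 from B4c, and the visit schedule from B4b.

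**1. Reproduce the plan's figure.** For a change score with first-to-last correlation r, the variance is 2(1 - r), and n per group = 2(1.96 + 0.8416)² x 2(1 - r) / 0.35² = 128.1 x 2(1 - r).

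Compound symmetry, r = 0.6: 128.1 x 0.80 = 102.5, and x 1.2 = 123.0. The plan's number is recovered.

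**2. Same endpoint under B4c's AR(1) 0.7.**

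- Three visits, r = 0.7² = 0.49: 128.1 x 1.02 = 130.7, and x 1.2 = about 157.
- Four visits, r = 0.7³ = 0.343: 128.1 x 1.314 = 168.4, and x 1.2 = about 202.

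**3. Power**, as Phi(0.35 / sqrt(2 x variance / n) - 1.96):

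| Completers per group | CS 0.6 | AR(1) 0.7, three visits | AR(1) 0.7, four visits |
|---|---|---|---|
| 103 (123 / 1.2) | 80% | 70% | 59% |
| 120 (150 recruited, 20% lost) | 86% | 77% | 66% |

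Recruiting 150 per group narrows the shortfall under AR(1) but does not close it.

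**4. Error rate if compound symmetry is fitted to AR(1) data.** The fitted model gives the change a variance of 2(1 - mean pairwise r), while the true variance is 2(1 - r between first and last visit). With model-based standard errors, two-sided error = 2[1 - Phi(1.96 x sqrt(model variance / true variance))].

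- Four equally spaced visits at 0.7: mean r = (3 x 0.7 + 2 x 0.49 + 0.343) / 6 = 0.5705. Model variance is 0.859 and true variance 1.314, so the SE ratio is 0.81 and the error 11.3%.
- Decay in calendar time (months 0, 3, 6, 12; 0.7 per 3 months): mean r = 0.4938, variances 1.012 and 1.520, error 11.0%.
- Three visits: mean r = 0.63, variances 0.74 and 1.02, error 9.5%.
- Lower correlation, since 0.7 is a ceiling: at 0.5 per visit, 9.2% with four visits and 8.4% with three.

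Simulation at 123 per arm agrees: 11.2%, 11.0% and 9.3% for the first three cases with complete data, and 11.1%, 11.1% and 9.4% with 20% dropout. The documents do not say what interval the 0.7 refers to. Read as a 6-month correlation, it gives 12.7%.

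**5. Other tests from the same misfitted model.** The month-12 difference in least-squares means rejects in 4.8-5.1% of null simulations. The joint group-by-time test rejects in about 5.4-6.3%. If time were entered as a linear trend, the slope contrast (-3, -1, 1, 3) over four visits has true variance 14.95 against 20 x 0.4295 = 8.59 in the model, an error of 13.7%.

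**6. A structure-free alternative.** Estimating the change variance without structure held 4.7-5.2% in four-visit simulations. Where compound symmetry was true, it gave 85.5% power against 85.8% at 123 per arm.

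**The case against.** A reader might infer that the planned primary test runs at about 11% false positives. The documents do not support that, for three reasons.

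- No section says compound symmetry will be fitted. It appears only as a sizing assumption, and the random-intercept model is one reading of an unspecified model.
- AIM 1 makes month 12 the primary time point for comparing least-squares means, and Hypothesis 1 is also framed as a comparison of groups at 12 months. That contrast keeps its 5% level under the same misfit. The joint interaction test, one natural reading of the power section, is barely inflated.
- Only one pairing of fit and truth inflates error. A matched fit gives 5.0%. An AR(1) fit to compound-symmetric data is conservative, at about 0.6% with four visits.

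It can also be said that B4c never mentions a change score. Its AR(1) 0.7 inputs come close to 123 for other analyses if attrition is handled as n / 0.8: 96.5 / 0.8 = 121 for the mean of three post-baseline visits, or 97.4 / 0.8 = 122 for a baseline-adjusted analysis at lag 2. B4c may therefore have sized a different comparison.

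All of this stands, and it limits the error-rate point to a conditional risk. It does not remove the sizing conflict. If the two sections sized different contrasts, the plan presents one number as though it answered both. The power section sizes change from baseline and AIM 1 asks about greater change, so the affected contrast is a live reading of the plan.

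**Conclusion.** The sizing conflict is established from the text and by arithmetic. For the change endpoint, 123 per group follows from compound symmetry at 0.6 but not from AR(1) at 0.7, which would need about 157 to 202. Under AR(1) 0.7, power with about 103 completers is about 70% or 59%. These figures assume equal variances at each visit, the normal approximation, the plan's own x 1.2 inflation, and correlation at its stated ceiling.

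The inflated error of about 8-11% is a risk created by under-specification, not a declared flaw. It needs a random-intercept or compound-symmetry fit, model-based standard errors, correlation decaying as in B4c (taken as 0.5 to 0.7 per visit), and the change-from-baseline contrast as the test. The plan leaves open whether those conditions will be met, and the structure could be chosen after the data are seen. This should be settled before analysis.

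**What to change.** In AIM 1 of the analysis plan, specify for the continuous LUP-QOL and PAM models that visit is categorical and that the within-woman covariance over baseline and months 3, 6 and 12 is unstructured. Alternatively, specify robust (sandwich) standard errors. Either should replace reliance on a random intercept alone with model-based standard errors. The degrees-of-freedom method and the fallback for non-convergence can be left to the trial statistician.

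In B4c and the Power and Sample Size Justification, state one contrast, one covariance structure, one correlation (with the interval it refers to) and one visit count. Then restate the power that follows, at both 123 and the planned 150 per group.

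The cost is wording plus a few covariance parameters: an unstructured four-visit matrix has 10, for about 300 women. The loss of precision if compound symmetry holds is negligible. The stated power may become less favourable once the assumptions are reconciled.

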
# B4. Approach

B4a. Theoretical Basis for Peer Mentoring

The Main Effect Model of Social Support posits that it is social relationships, and the support received from them, that are the primary drivers of improvements in both physical and mental health.99 The proposed peer mentoring intervention for African American women with SLE fits within a social support model that we hypothesize will influence this main effect by inducing downstream effects on health-related quality of life, mental well-being, and immune function, as it relates to disease activity. Within this model, we expect peer mentoring to reduce feelings of isolation and loneliness; provide culturally tailored, experiential, and evidence based education and information about accessing available health services; and promote behaviors that positively improve disease self-management, health-related quality of life, and disease activity.[86,100,101]

B4b. Study Overview. The Peer Approaches to Lupus Self-Management (PALS) study is a randomized controlled trial designed to examine whether a new, culturally tailored peer mentoring intervention improves disease self-management, indicators of disease activity, and health related quality of life (HRQOL) in African American women with systemic lupus erythematosus (SLE). African American women with active SLE will be recruited as mentees and peer mentors. We will recruit 300 mentees (150 mentored and 150 support group) and up to 60 mentors. As part of each wave, mentors (n=20) will be trained to deliver intervention content, prior to being paired with up to three mentees (n=50). The peer mentoring intervention will occur by twelve 60-minute telephone or video sessions carried out across the course of 24 weeks. In each wave, social support controls (n=50) will participate in a lupus support group

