#### Recruitment of Mentors

Potential peer mentors will first be invited from PALS pilot participants (mentees and mentors) (n=30), with the intention of retaining mentors to mentor multiple groups of mentees over the course of the study. It is expected that everyone would benefit from the use of experienced mentors, and using experienced mentors over time is also consistent with future real-world implementation. As needed (up to n=60, but approximately n=30 expected to be needed based on past research participation and interest), potential peer mentors who are considered competent in the management of their conditions will be identified by MUSC rheumatologists and subsequently trained by the PI. As part of the ongoing MUSC SLE database, patients are regularly flagged who providers deem competent enough to speak with the media on behalf of the patient population. We will mail out recruitment letters that will explain the study and provide participants a number to call if they are interested in participating. Participants who indicate interest in the study will be contacted by telephone to conduct a pre-screening assessment. If eligibility criteria are met, the screening/enrollment visit will be scheduled. As part of the mentor screening interview with the PI, psychosocial status will be assessed using the psychological scales of the Arthritis Impact Measurement Scales (AIMS), the Arthritis Helplessness Index (AHI), Wallston General Perceived Competence Scale, University of California at Los Angeles (UCLA) Loneliness Scale, Rosenberg Self-Esteem, Campbell Personal Competence Index. Carkhuff Communication and Discrimination Skills Inventories, and the Applied Knowledge Assessment (AKA) scale.[113] The PI will make a determination of competence, maturity, emotional stability, and verbal communication skills after overall assessment during the screening interview and training. Additional recruitment strategies will include the identification of local SLE support group members who have emerged as natural helpers, referrals from other rheumatologists and arthritis health professionals, and outreach to the local chapters of the Lupus and Arthritis Foundations by letter and telephone. Others have used these approaches successfully in multiple studies.

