**Data Collection Strategy** 

Data Collection Process/Schedule: Fourteen trained peer mentors will deliver the intervention in each wave and one full-time study coordinator (SC) will conduct screening, consent, enrollment procedures, and support group moderation. The primary method of data collection will be face to face interview. Mentees will be assessed at baseline, mid-intervention (3 months from baseline), immediately post-intervention (6 months from baseline), and 6 months post-intervention (12 months from baseline). Physical examination and laboratory evaluation will be achieved by in-person clinic visit when recent SLEDAI scores are not available in the database record of a given participant. Social support control participants will complete assessments on the same schedule as mentored participants. Given evidence that peer support may be just as beneficial to the supporters as it is to the person being supported, [118,119] mentors will be assessed on the same schedule as mentored and control participants, using the same tools.

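### Mentor clustering in the primary analysis is left unsettled: the optional mentor fixed effect is aliased with arm, the listed Aim 1 model has no mentor term, and the per-wave cluster size ignores mentor reuse

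*Combined protocol and SAP*

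**What the plan says.** The Power and Sample Size Justification paragraph deals with mentors in four steps.

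- It sets the correlation aside: "clustering within mentors and mentees are assumed to have minimal intra-class correlation based on pilot data". No figure is given.
- It supports this by cluster size: "especially since the cluster sizes would be at most 3 at a given wave".
- It then says: "However, a multi-level model will be used in the analysis to verify this".
- It closes with: "We will also consider including mentor as a fixed effect in the model". How control women would be coded, and whether mentor would interact with time, is not stated.

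The same paragraph equates the powered test with the time-by-group interaction.

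Under Overview of Statistical Analysis Plan, the Aim 1 model has time, treatment, their interaction and a list of covariates as fixed effects. Arm least squares means are compared at month 12, the primary time point. Mentor does not appear.

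The Control Intervention paragraph gives the comparison arm a coordinator-moderated support group and no mentors. Recruitment of Mentors plans to invite pilot participants first, "with the intention of retaining mentors to mentor multiple groups of mentees over the course of the study", and puts the number at "up to n=60, but approximately n=30 expected to be needed based on past research participation and interest". Enrolment is in three waves.

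**The concern.** Three things do not fit together.

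1. A factor that exists in one arm only cannot be a fixed effect beside arm without a linear dependency. The Aim 1 paragraph's named contrast is the arm difference at month 12, which is where the dependency falls.
2. Women who share a mentor may have correlated outcomes. If the primary model omits mentor, or treats mentors as fixed, the standard error of the arm difference is too small whenever that correlation is positive.
3. The case for ignoring the correlation rests partly on a per-wave cluster size, while the recruitment plan builds clusters across waves.

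At stake are the type I error and the confidence interval of the primary comparison. Three analyses (no mentor, multi-level, fixed mentor) also stay open, with different standard errors and no rule for choosing among them.

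**Working it through.** **Plan's own figure.** For change from baseline under compound symmetry with correlation 0.6, the variance of a change is 2(1 − 0.6) = 0.8 in SD² units. Then n = 2 × (1.960 + 0.842)² × 0.8 / 0.35² = 102.5 per arm, and 102.5 × 1.2 = 123.0. This reproduces the stated 123 per group with no allowance for mentor clustering.

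**Aliasing.** Take four visits, 30 mentors with 5 mentees each, and 150 controls with no mentor.

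- Mentor as a main effect: 1 intercept + 3 time + 1 arm + 3 arm-by-time + 30 mentor = 38 columns, rank 37. The arm coefficient is not estimable, nor is the month-12 arm difference with mentor held equal. The arm-by-month-12 interaction is estimable, and so is controls versus the average of the mentor means.
- Mentor-by-time added: 38 + 90 = 128 columns, rank 124. The arm-by-month-12 coefficient is now aliased too. The average-mentor contrast is still estimable.

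**Cluster size over the study.** 150 mentees over 60 mentors is 2.5 each; over 30 it is 5; over the same 20 in every wave it is 7.5. The ceiling is 3 per wave × 3 waves = 9.

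The per-wave cap is also in doubt. The Study Overview has 20 mentors for 50 mentees per wave, but the Data Collection Strategy says: "Fourteen trained peer mentors will deliver the intervention in each wave". Since 14 × 3 = 42 is fewer than 50, those two passages need to be reconciled.

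**Effect on the test.** The documents give no ICC, so 0.05 and 0.10 are assumptions, applied to the change score. Clustering is in the mentored arm only, with design effect D = 1 + (m − 1) × ICC.

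- True variance of the arm difference: 0.8 × (1 + D)/n.
- Type I error with mentor left out: 2[1 − Φ(1.96 × √(2/(1 + D)))].
- Type I error with mentor fixed, average-mentor contrast: 2[1 − Φ(1.96 × √((2 − ICC)/(1 + D)))].
- Power at n = 150 × 0.8 = 120 analysed per arm: Φ(0.35/√(0.8(1 + D)/120) − 1.96).

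| Mentees per mentor | ICC | D | Type I, mentor left out | Type I, mentor fixed | Power |
|---|---|---|---|---|---|
| any | 0 | 1.00 | 0.050 | 0.050 | 85.8% |
| 5 | 0.05 | 1.20 | 0.062 | 0.065 | 82.4% |
| 5 | 0.10 | 1.40 | 0.074 | 0.081 | 79.0% |
| 9 | 0.05 | 1.40 | 0.074 | 0.077 | 79.0% |
| 9 | 0.10 | 1.80 | 0.098 | 0.106 | 72.6% |

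At 5 per mentor and ICC 0.05, the correct standard error is √(2.2/2) = 1.049 times the unclustered one.

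**The case against.** The strongest reply has four parts.

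- **The main comparison is not lost.** A reader might infer that a mentor fixed effect makes the trial's primary result impossible to estimate. The documents do not support that. The power paragraph names the time-by-group interaction as the powered test, and it survives a mentor main effect. An average-mentor contrast survives either coding. This stands.
- **The fixed effect is only to be considered, whereas the multi-level model is stated firmly.** This stands in part. The multi-level model is introduced as a way to verify that the correlation is minimal. It has no stated random-effect structure, is not confined to one arm, and does not reach the Aim 1 model. The Aim 2 text mentions only correlation within participants, and the one reference to adjusting for clustering in the exploratory analyses concerns change scores.
- **The cluster limit is explicitly per wave.** This stands: the sentence is incomplete, not false. Nor does any passage say that a reused mentor would count as a new cluster in each wave.
- **Planned enrolment has slack.** With 150 per arm against 123 required, power is still about 82% at 5 per mentor and ICC 0.05. This stands for power, but extra enrolment does not correct a standard error that omits mentor.

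Larger effects could be had by supposing that the same 14 mentors serve all 150 mentees, or that one reference mentor is compared with all controls. The plan states neither, so neither is used here.

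**Conclusion.** The concern holds as a specification fault in the primary analysis, not as a claim that the arm effect cannot be estimated. The fixed-effect option is aliased with arm. Where a usable contrast remains, the average-mentor standard error leaves out between-mentor variance. The listed Aim 1 model has no mentor term, and the cluster-size argument does not describe the study-wide design.

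For an ICC of 0.05 to 0.10, type I error with mentor left out is about 0.062–0.074 at 5 per mentor and 0.074–0.098 at 9. Power falls from about 86% to 82–79% and 79–73%.

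These figures rest on the assumed ICC range, equal cluster sizes, and control women treated as independent. Nine per mentor is a ceiling that would need every mentor fully loaded in all three waves; five is the figure implied by the expected 30 mentors. Clusters are kept at enrolled size, so with 20% loss the effects would be somewhat smaller. At an ICC of 0.01 they are slight: type I error is 0.052 at 5 per mentor and 0.055 at 9.

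**What to change.** 1. In Power and Sample Size Justification, delete the option of mentor as a fixed effect.
2. In the Aim 1 analysis paragraph, turn the multi-level commitment into the primary model. Make it partially nested, with a random mentor effect in the mentored arm only, one mentor identifier carried across all waves, and small-sample degrees of freedom.
3. In the power paragraph, state an assumed ICC range and the expected total mentees per mentor over the study, and restate power on that basis. Reconcile the 20 and 14 mentors per wave at the same time.

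Settle this before outcome data by arm are seen. The cost is wording, plus a slightly wider confidence interval: the standard error is about 5% larger at 5 per mentor and ICC 0.05. At the far end of the range (9 per mentor, ICC 0.10) it is √(2.8/2) = 1.18 times as large.
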